11.1.4. Unanticipated Problems

11.1.4.1. Definition of Unanticipated Problems

Any incident, experience, or outcome that meets all the following criteria:

- Unexpected in terms of nature, severity, or frequency given (a) the research procedures that are described in the protocol-related documents, such as the IRB-approved research protocol and informed consent document, and (b) the characteristics of the participant population being studied; and
- Related or possibly related to participation in the research (“possibly related” means there is a reasonable possibility that the incident, experience, or outcome may have been caused by the procedures involved in the research); and
- Suggests that the research places participants or others (which many include research staff, family members or other individuals not directly participating in the research) at a greater risk of harm (including physical, psychological, economic, or social harm) than was previously known or expected.

The investigator is responsible for ensuring that the IEC/IRB is also informed of the unanticipated problem, in accordance with local regulations.

11.2. Toxicity Management

The investigator (or qualified designee) will grade clinically significant events and laboratory abnormalities (if considered AEs) as described in Section 11.1.1.4. Grade 3 and 4 clinically significant laboratory abnormalities should be confirmed by repeat testing and before any contemplated study drug discontinuation, unless such a delay is not consistent with good medical practice.

In the event that a new clinically significant safety signal emerges, a meeting of the DMC may be convened by the sponsor to evaluate risk to subjects and recommend appropriate actions. Based on the data presented, a decision will be made as to whether to halt the study, to continue dosing, or to continue dosing with provisions introduced into the protocol via substantial amendment.

11.2.1. Treatment Interruptions

Treatment interruptions as a result of investigator management of AEs potentially related to berotralstat are permissible. Resumption of berotralstat is also permissible upon resolution of the event, as assessed by the investigator, with a plan for stringent monitoring of the subject for recurrence of the AE as appropriate. In addition, other extenuating circumstances may lead to treatment interruptions such as vomiting during an abdominal HAE attack or required fasting for medical procedures; in these cases, berotralstat should be resumed once the extenuating circumstance is resolved. The sponsor medical monitor should be notified in the event of a treatment interruption due to an AE. Any treatment interruption will be recorded in the CRF and source documents, including the reason for the interruption.

Treatment interruptions due to confirmed QTcF > 500 msec or increase more than 60 msec from baseline associated with C_{max} exceeding the adult range are permissible. If interrupted, subjects may resume berotralstat at a reduced dose at the investigator's discretion. Subjects may remain on the reduced berotralstat dose if they no longer meet QTcF stopping criteria at steady state (see Section 7.3.2).

Other treatment interruptions may be permissible following consultation with the medical monitor.

11.2.2. Dose Reductions

Dose reductions are allowed based on emerging PK and/or safety data (see Section 8.4).

Dose reductions due to confirmed QTcF > 500 msec or increase more than 60 msec from baseline associated with C_{max} exceeding the adult range are permissible. Subjects may remain on the reduced berotralstat dose if they no longer meet QTcF stopping criteria at steady state (see Section 7.3.2).

If the berotralstat dose is reduced, see Section 10.9.1 for collection of PK samples.

Other dose reductions may be permissible following consultation with the medical monitor. The previous dose of berotralstat may be resumed upon resolution of the safety event at the discretion of the medical monitor based on PK and/or safety review (see Section 8.4).

11.2.3. Overdose

To date, there is no experience with overdose of oral berotralstat. Single doses of up to 1000 mg, 7 days of dosing up to 500 mg/day, and 14 days of dosing with 350 mg/day revealed no clinically significant safety concerns in healthy subjects. Safety data generated in Study BCX7353-203 with 28-day dosing of up to 350 mg/day revealed no clinically significant safety concerns in subjects with HAE. Subsequently, subjects enrolled in Study BCX7353-106 were exposed to berotralstat 450 mg QD for 14 days without any unanticipated AEs or increased AE severity.

In the event that study personnel become aware of an overdose of berotralstat (> 1 dose per calendar day) that is associated with an AE, both the overdose and the resultant event should be reported as AEs. An overdose without associated signs or symptoms should not be recorded as an AE but should be reported as a protocol deviation.

If an overdose occurs with or without associated AEs, subjects should undergo clinical and laboratory monitoring as appropriate for their clinical condition and, if indicated, should receive clinically indicated supportive therapy.

Overdose will be considered an SAE only if any of the seriousness criteria are met. Any clinical complication in association with the overdose should be reported as an AE and, where applicable, SAE along with the overdose (see Section 11.1.3). Details of signs or symptoms, clinical management, and outcome should be included in the AE report, if available.

Additional information about overdose as an AE or SAE is discussed in Section 11.1.1.2.

11.3. Data Monitoring Committee

An independent DMC will be established for interim safety monitoring. The specific responsibilities and composition of the DMC are outlined in a separate DMC charter. The charter will include, at a minimum, a description of DMC membership, roles, timing of DMC review and responsibilities of DMC members. In addition, the details of outputs provided for the meetings will be referenced in this charter.

The DMC will be convened according to FDA guidelines. In general, the DMC will review safety data on an ongoing basis and SAEs considered related to berotralstat as they occur. Prior to initiating dosing with berotralstat (ie, initiation of Part 1) in Cohorts 3 and 4 (and any subsequent cohorts), the DMC will meet and review safety data and endorse opening of all subsequent cohorts.

11.4. COVID-19

The study will be conducted in accordance with relevant local, regional, and national guidance around coronavirus disease 2019 (COVID-19). In order to minimize the risk of COVID-19 transmission, additional procedures or assessments (which may include but are not limited to symptom assessment, temperature assessment, and viral ribonucleic acid testing) may be implemented at the discretion of the investigator beyond those required in this protocol. Study visits or procedures may be modified in accordance with relevant local, regional, and national guidance as necessary to preserve subject safety during trial conduct. All protocol deviations resulting from COVID-19 will be identified as such. All study activities will be conducted in accordance with relevant local, regional, and national guidance around COVID-19.

12. STATISTICS

12.1. Sample Size Considerations

The study is designed to evaluate the PK and safety/tolerability of oral administration of berotralstat in pediatric subjects ages 2 to < 12 years of age who have HAE. A sample size of approximately 30 subjects enrolled in 4 or more cohorts is adequate to evaluate the PK and to describe safety and tolerability. The sample size was selected based on feasibility considerations; however, with 30 subjects enrolled in the study, there is an approximately 96% chance of observing at least 1 treatment-emergent adverse event (TEAE) that occurs 10% of the time. Formal inferential testing of effectiveness and safety endpoints is not planned.

12.2. Statistical Methods

A detailed statistical analysis plan (SAP) will be developed to describe the methods of analyses and summaries, including all endpoints, time points, populations, missing data, prior to the review of any data. Deviations from the analyses outlined in the SAP will be described in the clinical study report.

12.2.1. Analysis Populations

The analysis populations are defined in subsections that follow.

12.2.1.1. Intent to Treat Population

The intent to treat (ITT) population will include all subjects who satisfy all entry criteria and who enroll into the study. As this study focuses on safety and PK of berotralstat, analyses of the ITT population will likely be limited.

Note that subjects for whom their P/C provided written informed consent but who are not enrolled in the study will be considered screen failures. Subjects who are “preliminary enrollees” awaiting final confirmation of eligibility will also be considered screen failures if found to be ineligible for study participation.

12.2.1.2. Completer Population

For study Parts 1 and 2, the subset of subjects who complete the 12 and 48 weeks of dosing may be analyzed for a subset of effectiveness endpoints.

12.2.1.3. Safety Population

The safety population will include all subjects who received at least 1 dose of berotralstat. This population will be used for analyses of accountability, demographics, berotralstat drug dosing and compliance, and safety. Effectiveness endpoints will also be summarized using this population.

12.2.1.4. PK Population

The PK population will include subjects in the safety population who have at least one dose of the study medication and had at least one evaluable and quantifiable post-dose PK sample obtained.

12.2.2. General Considerations for Data Analysis

Descriptive statistics will be used to summarize the data from this study. Data will be summarized by cohort, overall, and by study day or time, if appropriate. Unless stated otherwise, the term “descriptive statistics” refers to number of subjects (n), mean, standard deviation (SD) or standard error of the mean (SEM), median, minimum, and maximum for continuous data, and frequencies and percentages for categorical data. For TEAE data, both the number of subjects and total number of events will be reported. For PK endpoints, please see Section [12.2.4](#) for further details.

Data summaries will be provided to the DMC as specified in the DMC Charter. Interim analysis of PK, safety, and effectiveness data may be conducted after at least 15 subjects complete

48 weeks of treatment (Part 2) and/or after all subjects complete 48 weeks of treatment. Additional interim analyses may be performed during the course of the study as needed to support regulatory filings, safety updates, and publications, as documented in the SAP. Effectiveness data are not collected after Week 48. Disposition and safety data will be summarized through the end of study (Week 144).

The final analysis of disposition, dosing, and safety data collected in Parts 1, 2, and 3 will be conducted once the last subject completes or discontinues his or her respective parts, the resulting clinical database has been cleaned and quality checked, the analysis populations have been finalized, and after database lock has occurred. Disposition, dosing, and safety data will be summarized through the end of study (Week 144).

Data collected during the study will be included in data listings as measured or recorded in patient diaries. Unless otherwise noted, data listings will be sorted by subject and study visit/date.

Statistical analyses will be conducted using SAS® software version 9.2 or higher (SAS Institute, Cary, North Carolina, US). All analyses will be subject to formal verification procedures. All tables and figures generated to summarize data will be reviewed by the lead statistician to ensure accuracy and consistency of analyses; the lead clinical pharmacologist will review data summarized for the PK endpoints to ensure their accuracy and consistency.

12.2.3. Subject Demographic and Disposition Data

Demographic data and baseline characteristics including age, gender, race, ethnicity, height, weight, BMI, and HAE history, including medication history, will be summarized by weight cohort and for all subjects.

Subject disposition will be presented for all subjects. The number of subjects who complete each study part as well as the entire study and those who discontinue from the study will be provided. The reasons for early discontinuation will be presented. A tabulation of the number of subjects exposed to berotralstat and the duration of exposure will also be presented. Treatment adherence, dose interruptions, and reason for dose interruptions will be provided as summaries or listed as appropriate.

12.2.4. Pharmacokinetic Analyses

Plasma samples for determination of berotralstat concentrations are planned to be collected at times indicated in the Schedule of Assessments. All plasma concentrations that are part of the PK population will be incorporated into the population PK analyses.

The results of these analyses will be reported in a separate pharmacometric report.

12.2.5. Analysis of Safety Variables

Adverse events will be mapped to the Medical Dictionary for Regulatory Activities (MedDRA) preferred term and system organ classification. The occurrence of TEAEs will be summarized using MedDRA preferred terms, system organ classifications, and severity (eg, Grade 3 or 4) by cohort and for all subjects. Separate summaries of treatment-emergent SAEs and AEs related to study drug will be generated, as well as AEs leading to study drug being interrupted or study withdrawal. All AEs will be listed for individual subjects showing both verbatim and preferred

terms. Adverse events that are reported during the SOC treatment period will be summarized separately.

Descriptive summaries of clinical laboratory results will be presented by study visit by cohort. Laboratory abnormalities will be graded according to the DAIDS Table for Grading Adverse Events for Adults and Pediatrics (Corrected Version 2.1, July 2017) unless otherwise specified. In addition to DAIDS requirements, creatinine increases from baseline must also meet certain minimum thresholds, to appropriately target meaningful changes in creatinine in pediatric patients with low baseline values, as summarized below:

- Grade 1 mild: 1.1 to 1.3 x ULN OR increase ≥ 0.2 mg/dL from participant's baseline
- Grade 2 moderate: > 1.3 to 1.8 x ULN OR increase ≥ 1.3 x baseline AND increase ≥ 0.3 mg/dL from baseline
- Grade 3 severe: > 1.8 to 3.5 x ULN OR increase ≥ 1.5 x baseline AND increase ≥ 0.5 mg/dL from baseline)
- Grade 4 potentially life threatening: > 3.5 x ULN OR Increase ≥ 2 x baseline AND increase ≥ 0.7 mg/dL from baseline

The number and percentage of subjects experiencing treatment-emergent graded toxicities will be summarized. Laboratory toxicity shifts from baseline to post-baseline assessments will be summarized or listed by cohort.

Effects of berotralstat on pediatric patient growth (weight, height, and BMI) will be assessed over time by cohort. Vital signs, laboratory data (eg, chemistry, hematology, and urinalysis results), and ECGs will also be summarized over time by cohort.

Previous and concomitant medications will be mapped to a World Health Organization preferred term and drug classification. The number and percentage of subjects taking concomitant medications will be summarized using preferred terms and drug classifications (including during the SOC treatment period).

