The berotrastat dose for Part 1 will be determined based on subject weight on Day 1; this dose will be changed for an individual subject or for all subjects in the cohort if indicated by safety and/or PK parameters. In Parts 2 and 3, subjects will continue open-label berotrastat for a total of up to an additional 132 weeks. The dose in Parts 2 and 3 will be based on subject weight and may be adjusted throughout the 132-week treatment period as indicated based on changes in the subject's weight, safety, and/or PK parameters.

Cohort	Dose	Minimum Target Enrollment ^a	Weight Band (from PK modelling)
1	150 mg capsule	n = 4	≥ 40 kg
2	108 mg granules	n = 4	32 to < 40 kg
3	96 mg granules	n = 4	24 to < 32 kg
4	78 mg granules	n = 3	12 to < 24 kg

Note: Additional dose strengths ranging from 60 to < 150 mg and/or cohorts may be utilized as indicated based on safety and/or PK results.

^a The n represents the minimum number that will be enrolled into each cohort. Since the total target enrollment is approximately 30 subjects, additional subjects will be enrolled into one or more of the cohorts or additional dose cohort(s) may be added. Subject enrollment in any one or more cohorts may be suspended to ensure sufficient enrollment of subjects in each cohort.

Reference therapy, dosage, and mode of administration:

This is an open-label trial, and there is no reference therapy. Subjects will remain on their SOC regimen for the 12 weeks comprising the SOC treatment period. SOC may include short-term prophylaxis, long-term prophylaxis, and/or on-demand treatment for acute attacks. Data on AEs and HAE attacks will be collected during this period.

Duration of treatment:

Subjects will continue to take their SOC for 12 weeks following screening. Subjects who continue in the study will take berotrastat capsules (150 mg) or granules for oral administration (in unit-dose packets) for 12 weeks (Part 1) beginning on Day 1. For Parts 2 and 3, subjects will take berotrastat through Weeks 48 (Part 2) and 144 (Part 3), respectively.

Criteria for evaluation:

Pharmacokinetics (PK):

Plasma PK concentrations will be used in the population PK analysis.

Safety:

Frequency and severity of AEs/SAEs, laboratory analyses (clinical chemistry, hematology, coagulation), height, weight, vital signs, ECGs, and physical examinations.

Effectiveness:

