5.2.2. Secondary Endpoints

The secondary endpoint of safety will be measured by frequency and severity of adverse events (AEs) and serious adverse events (SAEs), laboratory analyses (clinical chemistry, hematology, coagulation), height, weight, vital signs, electrocardiograms (ECGs), and findings from physical examinations.

Safety endpoints will be assessed at the end of each Part (ie, Weeks 12, 48, and 144/end of study [EOS]).

The other secondary endpoint of effectiveness will be measured by assessing the frequency of attacks, duration of symptoms, anatomical location, on-demand treatment required, number of days with angioedema symptoms, assessment of attack severity, discontinuations due to lack of efficacy, and number of hospitalizations and clinic visits from Week 1 through Weeks 12 and 48.

[figure not shown]

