10.1. Demographics

Demographic information, including month and year of birth, sex, race, and ethnicity (as applicable or as permissible by country requirements) will be captured for each subject participating in the study at the screening visit. Medical and medication history will be captured at the screening visit and updated at enrollment (if different from the screening visit).

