Serum Sickness¹⁰	Mild signs and symptoms	Moderate signs and symptoms AND Intervention indicated (e.g., antihistamines)	Severe signs and symptoms AND Higher level intervention indicated (e.g., steroids or IV fluids)	Life-threatening consequences (e.g., requiring pressor or ventilator support)
Underweight¹¹ > 5 to 19 years of age	WHO BMI z-score < -1 to -2	WHO BMI z-score < -2 to -3	WHO BMI z-score < -3	WHO BMI z-score < -3 with life-threatening consequences
2 to 5 years of age	WHO Weight-for-height z-score < -1 to -2	WHO Weight-for-height z-score < -2 to -3	WHO Weight-for-height z-score < -3	WHO Weight-for-height z-score < -3 with life-threatening consequences
< 2 years of age	WHO Weight-for-length z-score < -1 to -2	WHO Weight-for-length z-score < -2 to -3	WHO Weight-for-length z-score < -3	WHO Weight-for-length z-score < -3 with life-threatening consequences
Unintentional Weight Loss (excludes postpartum weight loss)	NA	5 to < 9% loss in body weight from baseline	≥ 9 to < 20% loss in body weight from baseline	≥ 20% loss in body weight from baseline OR Aggressive intervention indicated (e.g., tube feeding, total parenteral nutrition)

¹⁰ Definition: A disorder characterized by fever, arthralgia, myalgia, skin eruptions, lymphadenopathy, marked discomfort, and/or dyspnea.

¹¹ WHO reference tables may be accessed by clicking the desired age range or by accessing the following URLs:
http://www.who.int/growthref/who2007_bmi_for_age/en/ for participants > 5 to 19 years of age and
http://www.who.int/childgrowth/standards/chart_catalogue/en/ for those ≤ 5 years of age.

Urinary

PARAMETER	GRADE 1 MILD	GRADE 2 MODERATE	GRADE 3 SEVERE	GRADE 4 POTENTIALLY LIFE- THREATENING
Urinary Tract Obstruction	NA	Signs or symptoms of urinary tract obstruction without hydronephrosis or renal dysfunction	Signs or symptoms of urinary tract obstruction with hydronephrosis or renal dysfunction	Obstruction causing life-threatening consequences

Site Reactions to Injections and Infusions

PARAMETER	GRADE 1 MILD	GRADE 2 MODERATE	GRADE 3 SEVERE	GRADE 4 POTENTIALLY LIFE- THREATENING

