11.6. Vital Signs

Descriptive summaries of vital signs (blood pressure, temperature, pulse, respiratory rate, height, weight, BMI) and change from baseline vital signs will be presented by parameter, time point, and cohort. Vital signs and physical examination results will each be listed by cohort, subject, and time point.

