X	X	X	14.3.1.13.4	Subjects Reporting Treatment-emergent Adverse Events in the Hypersensitivity, Anaphylactic Reaction or Severe Cutaneous Reaction SMQs	Safety
X	X	X	14.3.1.14	Subjects Reporting Treatment-emergent Adverse Events in the Torsade de pointes/QTc Prolongation SMQ or Palpitation Preferred Term	Safety
X	X	X	14.3.1.15	Overall Summary of Adverse Events During the SOC Treatment Period	Safety
X	X	X	14.3.1.16	Subjects Reporting Adverse Events During the SOC Treatment Period by MedDRA System Organ Class and Preferred Term	Safety
X	X	X	14.3.4.1.1	Summary of Observed and Change from Baseline in Clinical Chemistry Laboratory Parameters	Safety
X	X	X	14.3.4.1.2	Summary of Observed and Change from Baseline in Hematology and Coagulation Laboratory Parameters	Safety
X	X	X	14.3.4.1.3	Summary of Observed and Change from Baseline in Quantitative Urinalysis Laboratory Parameters	Safety
X	X	X	14.3.4.2.1	Summary of Elevations in Post-Baseline Liver Function Tests	Safety
X	X	X	14.3.4.2.2	Hy's Law Plot of Maximum Total Bilirubin vs. Maximum ALT	Safety

NDA IA	End of Part 2 (Wk 48) IA†	Final/ EOS**	Output Number	Title	Population
X	X	X	14.3.4.2.3	Liver Test Safety Panel Over Time, Baseline vs. On-Study	Safety
X	X	X	14.3.4.2.4	Distribution of Liver Tests Over Time: ALT, AST, ALP, and Bilirubin	Safety
X	X	X	14.3.4.3	Treatment-Emergent Grade 3 and 4 Laboratory Toxicities by DAIDS Grades*	Safety
X	X	X	14.3.4.4.1	Shift from Baseline to Worst Post-baseline Assessment: Clinical Chemistry	Safety
X	X	X	14.3.4.4.2	Shift from Baseline to Worst Post-baseline Assessment: Hematology and Coagulation	Safety
X	X	X	14.3.4.4.3	Shift from Baseline to Worst Post-baseline Assessment: Urinalysis	Safety
X	X	X	14.3.5.1.1	Observed and Change from Baseline in 12-Lead ECG	Safety
X	X	X	14.3.5.1.2	12-Lead ECG Interpretation	Safety
X	X	X	14.3.5.1.3	12-Lead ECG QTcF Interval Categories	Safety
X	X	X	14.3.5.2.1	Observed and Change from Baseline in Vital Signs	Safety
X	X	X	14.3.5.3.1.1	Plot of Mean (SD) QTcF Observed Changes Relative to Baseline Over Time	Safety
X	X	X	14.3.5.3.1.2	Distribution Plots for QTcF Observed Changes Relative to Baseline Over Time	Safety
X	X	X	14.3.5.3.1.3	Distribution Plots for QTcF Observed Changes Relative to Baseline – All Observations	Safety
X	X	X	14.3.5.3.2.1	Plot of Mean (SD) PR Interval Observed Changes Relative to Baseline Over Time	Safety
X	X	X	14.3.5.3.2.2	Distribution Plots for PR Interval Observed Changes Relative to Baseline Over Time	Safety

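### Growth is to be assessed only as raw height, weight and BMI change, with no age- and sex-specific reference, so a moderate slowing could not be told from normal growth

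*Protocol*

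**What the plan says.** Protocol section 12.2.5 states: "Effects of berotralstat on pediatric patient growth (weight, height, and BMI) will be assessed over time by cohort". It names no metric and no reference population. Height and weight also belong to the secondary safety endpoint in Protocol section 5.2.2, which lists "height, weight, vital signs, electrocardiograms (ECGs), and findings from physical examinations".

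The SAP fills in the method in section 11.6, where these measures sit among the vital signs: "height, weight, BMI) and change from baseline vital signs will be presented by parameter, time point, and cohort". In SAP Table 7 the matching output is 14.3.5.2.1, titled "Observed and Change from Baseline in Vital Signs", supported by listing 16.2.8.5. Neither the SAP text nor Table 7 contains a growth z-score, percentile, velocity or reference population. SAP sections 8.2 and 8.3 rule out covariate adjustment and subgroup analyses.

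On comparison, the Protocol synopsis says: "This is an open-label trial, and there is no reference therapy". Protocol section 4.4.4 does call the 12-week standard-of-care period a control for safety, but the SAP plans no growth comparison against it. SAP section 6.6 sets baseline at the last value before the first dose.

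The data for a standardised analysis are collected. Protocol section 10.1 records "Demographic information, including month and year of birth, sex, race, and ethnicity", and footnote g of Protocol Table 2 schedules height and BMI at screening, Day 1, Weeks 12, 24, 36, 48, 72, 96, 120 and 144, and the end-of-study visit, with weight at every visit.

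**The concern.** A raw change from baseline is interpretable when the expected change without a drug effect is roughly zero, as for blood pressure or an ECG interval. Height and weight in children do not meet that condition: the expected change is positive, and its size depends on age and sex. The cohorts are weight bands, so each mixes ages and sexes, and the planned table gives no expected value beside the observed one.

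The stake is a safety question that the protocol itself poses for children followed on drug for up to 144 weeks. A moderate slowing of growth would appear as a positive mean change, and the reader of the table would have nothing to hold it against.

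**Working it through.** The plan states no figure for growth, so there is none to reproduce. (Its one computed probability, about 96% for seeing a 10% adverse event among 30 subjects, does reproduce as 1 − 0.9^30 = 0.958, but has no bearing here.)

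**1. Expected weight gain without a drug effect, from the protocol's own percentiles.** Protocol section 4.4.3 gives the median girl as 11 kg at about 2 years and about 40 kg at 12 years.

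- Average gain: (40 − 11) / 10 = 2.9 kg/year. This is a straight-line average; true gain varies with age.
- Time: weeks × 7 / 365.25, so 12, 48 and 144 weeks are 0.23, 0.92 and 2.76 years.

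| Week | Expected gain | Slowed 10% | Slowed 20% | Slowed 30% |
|---|---|---|---|---|
| 12 | 0.67 kg | 0.60 | 0.53 | 0.47 |
| 48 | 2.67 kg | 2.40 | 2.13 | 1.87 |
| 144 | 8.0 kg | 7.2 | 6.4 | 5.6 |

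Every entry is a gain. Without an age- and sex-specific expectation, 6.4 kg at Week 144 does not reveal itself as slow.

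**2. Age mix within a cohort.** At 2.9 kg/year, the 12 to < 24 kg band covers 12 / 2.9 = 4.1 years of median growth, and each 8 kg band covers 8 / 2.9 = 2.8 years. Children above or below the median widen the age range further.

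**3. Height (velocity assumed; the documents give none).** At 5 to 7 cm/year the gain over 144 weeks is 5 × 2.76 = 13.8 cm to 7 × 2.76 = 19.3 cm. Over the 12-week standard-of-care period it is only about 1.1 to 1.6 cm, too little for a usable growth-rate control.

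**4. Size of a slowing on the z-score scale (all assumed).** Take a slowing of 1 cm/year and a population height SD of 5 to 6 cm.

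- Week 144: 2.76 cm, or 2.76/6 = 0.46 to 2.76/5 = 0.55 SD.
- Week 48: 0.92 cm, or 0.92/6 = 0.15 to 0.92/5 = 0.18 SD.

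**5. Precision of a mean z-score change.** The 95% half-width is t(0.975, n − 1) × SD / √n. The SD of z-score change is assumed at 0.2 to 0.5. The sizes are the minimum cohorts (3 and 4), the minimum number completing Week 48 (15) and the planned total (30).

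| n | SD 0.2 | SD 0.3 | SD 0.5 |
|---|---|---|---|
| 3 | 0.50 | 0.75 | 1.24 |
| 4 | 0.32 | 0.48 | 0.80 |
| 15 | 0.11 | 0.17 | 0.28 |
| 30 | 0.07 | 0.11 | 0.19 |

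If children track their own centile, the mean z-score change expected without a drug effect is about 0. That gives the table the reference value it now lacks. Pooled, the estimate is informative; at 3 or 4 children it is weak.

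**The case against.** Three stronger readings are tempting, and the documents support none of them.

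- **That the planned table could show no growth effect at all.** Weight loss, stalled height or falling BMI would appear in the raw by-visit summaries and in listing 16.2.8.5. The DAIDS table in Protocol Appendix 15.1 also grades individual underweight by z-score (for the older children, Grade 1 is "WHO BMI z-score < -1 to -2") and unintentional weight loss as a percentage of baseline. These catch thinness or actual loss. The table has no row for height, so slowed but proportionate growth would not be graded. Nor is a positive change assured for BMI, which is a ratio and need not rise.
- **That there is no comparator of any kind.** The protocol names the standard-of-care period as a safety control, and height and weight are measured at screening and Day 1. What stands is that 12 weeks is too short for growth, and that the baseline rule keeps screening-to-Day 1 growth out of the change scores.
- **That z-scores would demonstrate a drug effect.** They compare children with a reference population. In a single-arm study, disease, earlier prophylaxis (SAP section 9.6 lists androgens) and pubertal timing remain confounded with treatment.

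Other points on that side also have weight. The study is descriptive with a PK primary objective, and the documents name no growth signal. The inputs are kept, so z-scores could be derived later. The figure of about 0.5 SD needs the full 144 weeks, while Part 3 may end early once another supply route exists (Protocol section 7.4). The table shells are in a separate document (SAP section 14.2), so the absence of a growth reference is established for the SAP text and Table 7 only.

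These points limit the size of the concern. They do not supply the missing reference.

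**Conclusion.** The concern holds in a limited form. The protocol undertakes to assess effects on growth, and the SAP provides raw values and raw changes by weight cohort with no age- and sex-specific reference and no adequate comparator. Gross failure would show; a moderate slowing would not be separable from normal growth.

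The weight figures (about 2.9 kg/year, and 8.0 kg against 6.4 kg at Week 144 under a 20% slowing) rest on the protocol's percentiles and a straight-line average. The height and z-score figures rest on assumed velocities and SDs: 1 cm/year would amount to roughly 0.46 to 0.55 SD at Week 144, but only 0.15 to 0.18 SD at Week 48.

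This is a cheap improvement to a secondary safety analysis. It does not touch the primary PK objective, and no data would be lost if it were made late. Setting it in the SAP now avoids choosing the reference after the data have been seen.

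**What to change.** In SAP section 11.6 and output 14.3.5.2.1:

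- Add height-, weight- and BMI-for-age z-scores at each visit with a height measurement, from one named reference. The CDC charts already serve the protocol's dose and weight-range rationale. The reference must cover age 2 to about 15, since a child enrolled just under 12 could be followed for 12 + 144 = 156 weeks, or about 3 years. State how age is derived from month and year of birth.
- Report change in z-score from Day 1 for all subjects pooled, as the main row, and by cohort, with 95% confidence intervals labelled descriptive. This is consistent with the absence of formal testing.
- Add individual z-score plots that include the screening value.
- Keep the raw summaries. Height and weight are named safety measures, and weight determines cohort and dose.
- Do not add a count of children falling by a fixed amount such as 0.5. The documents give no source for a cut-off. With no drug effect, a normal distribution and an assumed SD of change of 0.3 to 0.5, about 5% to 16% would cross it by chance, or 1.4 to 4.8 of 30.
- State that the z-scores are an external reference, do not establish a drug effect in a single-arm study, and are imprecise at 3 to 4 children per cohort (at an assumed SD of 0.3, a half-width of 0.48 at n = 4 against 0.17 at n = 15 and 0.11 at n = 30).

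The cost is one standard derivation, a few table rows and a figure. No new data are needed.
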